4.6 Hospitalization during Treatment

Adolescents will be followed by their medical doctor during treatment; this is usually adolescent medicine at CHOP. Should the medical doctor determine that the adolescent needs to be hospitalized for medical stabilization, this recommendation will be followed. Adolescents will be allowed to return to the trial post-hospitalization. Eating disorder symptomatology and weight will be assessed post-discharge from hospital. Any medication changes/additions will be noted. If, however, the adolescent needs to be referred to a higher level of care (e.g., inpatient treatment), then the adolescent will be removed from treatment in the trial.

4.7 Subject Completion/Withdrawal

Subjects may withdraw from the study at any time without prejudice to their care. They may also be discontinued from the study at the discretion of the Investigator for lack of adherence to study treatment or visit schedules, AEs, or due to need to refer to a higher level of care (inpatient or residential treatment). The Investigator may also withdraw subjects who violate the study plan, or to protect the subject for reasons of safety or for administrative reasons. It will be documented whether or not each subject completes the clinical study. If the Investigator becomes aware of any serious, related adverse events after the subject completes or withdraws from the study, they will be recorded in the source documents and on the case report form.

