1.2.2 Cognitive Remediation Therapy

CRT is an adjunctive intervention focusing on the development of meta-cognition – teaching individuals to think about how they think.⁴⁴ It involves presenting individuals with a variety of

tasks requiring increasingly complex mental abilities – these include geometric figures, illusions, reversing sequences of numbers and letters, completing sorting tasks wherein the rules change, and finding various routes on a map.⁴⁵ Most importantly, CRT focuses on process instead of outcome. That is, instead of focusing on whether or not a task was accurately completed, individuals in CRT are asked to think about how they solved a puzzle, reflect on their thought processes, and identify steps in problem solving. CRT has three goals:

1. Improve brain function by exercising and increasing connections in the brain
2. Encourage individuals to think about their thinking style
3. Encourage individuals and families to spend time away from thinking about the eating disorder.

CRT can be delivered in individual, family, and group formats.⁴⁶⁻⁴⁸ For this study, we will administer CRT to either adolescents or their parents. CRT will be delivered for 45-60 minutes prior to FBT sessions for a total of 15 sessions. Participants in CRT will be given weekly homework.

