4.8 Early Termination Study Visit

Subjects who withdraw from the study will be asked complete the full questionnaire battery. Should the family not wish to complete these measures, data from their last visit will serve as the last data point.

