6 STATISTICAL CONSIDERATIONS

6.1 Primary Endpoint

Aim 1: To identify whether or not it more impactful to add a parent or adolescent component of CRT to standard FBT. To assess if CRT engages the target, we will use mixed 3 (treatment) x 2 (time) Multivariate Analysis of Covariance (MANCOVA): one for adolescents, one for mothers, and one for fathers. The covariate for all analyses is total IQ on the WASI. Dependent variables are as follows: Trails Number-Letter Sequencing, Inhibition, Inhibition/Switching, Correct Response Shifting, Category Switching, or Description 1 or 2 and Shift on the BRIEF-2. We will follow these steps:

1. Conduct omnibus MANCOVA and evaluate significance. If not significant, stop and move to next analysis.
2. If the omnibus test is significant, we will conduct individual 2 (treatment) X 2 (time) Analysis of Covariance (ANCOVA) to determine which dependent variable had significant change, with IQ again as the covariate.
3. Each assessment of the target (DV) will be examined. Results will inform the Go/No-Go Decision as described in Table 6.

These three steps will be repeated for adolescents, mothers, and fathers. We will include all three groups in the initial MANCOVA and follow-up with planned comparisons (ANCOVA) of FBT vs the appropriate CRT condition. In all analyses, we will focus on the within and between-group effects, examining interaction effects are not necessary to evaluate the target. As we have chosen measures demonstrated to change with CRT,^{40,87-90} we will maintain $\alpha=0.15$ for each analysis.⁹¹ We do not expect adolescents whose parents receive CRT or parents whose adolescents receive CRT to demonstrate increases in flexibility. However, should the planned ANCOVAs not be significant, we will be able to explore other possible group differences. Additionally, we will explore the relationship between dependent variables via discriminant analysis. These additional methods to examine the data will not factor into the Go/No-Go decision, but will enhance the depth of our understanding of the data and contribute to our understanding of neurocognition in AN.

Aim 2: To determine the dose of CRT needed to lead to a medium effect size. Some research indicates that ≥ 8 sessions of CRT are necessary for improvement in cognitive flexibility with AN.⁹² It is unknown how many sessions will be needed for significant change in parents of

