9.4.4 Risk-Benefit Assessment

Risks are minimal. All adolescents will receive family-based treatment – the most recommended treatment for adolescents with AN. Two groups will receive an additional session of CRT each week. Adolescents will be required to have medical care during the course of the study. If they are not improving, recommendations for a higher level of care will be given. The benefits of finding a way to improve outcomes out-weighs the minimal risk.

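### Sections 4.6 and 4.7 disagree on whether referral to a higher level of care ends trial treatment or study participation, and no section clearly keeps removed adolescents or their parents in the D-KEFS testing that Aim 1 needs

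*Combined protocol and SAP*

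**What the plan says.** Three sections deal with early exit.

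- **Section 4.6** (hospitalization): an adolescent admitted for medical stabilization may come back to the trial. If a higher level of care is needed, "then the adolescent will be removed from treatment in the trial". Non-adherence is not mentioned, and neither is continued assessment of the adolescent or the parents.
- **Section 4.7** (completion and withdrawal): "They may also be discontinued from the study at the discretion of the Investigator for lack of adherence to study treatment or visit schedules". Further grounds in that sentence are adverse events and discontinuation "due to need to refer to a higher level of care (inpatient or residential treatment". The section then adds safety and administrative grounds. It speaks of subjects, not families.
- **Section 4.8** (early termination): "Subjects who withdraw from the study will be asked complete the full questionnaire battery". If the family declines, "data from their last visit will serve as the last data point".

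Section 9.4.4 says of adolescents in the trial: "If they are not improving, recommendations for a higher level of care will be given".

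The Aim 1 dependent variables in section 6.1 are "Trails Number-Letter Sequencing, Inhibition, Inhibition/Switching, Correct Response Shifting, Category Switching, or Description 1 or 2 and Shift on the BRIEF-2". They are analysed separately for adolescents, mothers and fathers, and section 6.4 specifies baseline and end of treatment as the two time points.

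**The concern.** For one event, referral to a higher level of care, 4.6 ends treatment and is worded as mandatory, while 4.7 ends study participation and is worded as optional. Staff following one section would act differently from staff following the other. Section 4.7 also allows study discontinuation for poor adherence, with no threshold. Section 7.1 has the PI supervise the therapists, and sections 3.2 and 9.1.2 blind only the assessors, so the decision can be made with knowledge of the arm.

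At stake is the Aim 1 endpoint. Section 9.4.4 ties referral to lack of improvement, so the missing scores would not be a random subset. Mothers and fathers have their own Aim 1 analyses. An adolescent's referral does not in itself prevent a parent from being tested, but nothing says that the parent's testing goes on.

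**Working it through.** **1. Which assessments survive removal?**

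- D-KEFS testing falls at intake and at Visits 9, 13 and 18 (sections 4.1 and 4.2.3 to 4.2.5). The 3- and 6-month follow-ups (T6 and T7 in 3.3.1) consist of chart review and questionnaires.
- Section 4.8 requests the questionnaire battery. By Table 1 this includes BRIEF-2, so BRIEF-2 Shift can be kept. The D-KEFS variables cannot be obtained this way.
- Section 4.8 is worded for those who withdraw. Whether it reaches subjects discontinued by the investigator is not stated.
- Section 3.1.5 sets the End of Treatment Evaluation in a 14-day window after treatment stops and has it mirror the intake. That could be read to include early stoppers. Section 4.2.5, however, fixes this evaluation as Visit 18, and 4.8 gives early leavers something different.

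No section therefore clearly provides end-of-treatment D-KEFS scores for a removed adolescent or for that adolescent's parents.

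**2. Planned loss.** Section 3.3.2 gives 60 enrolled and at least 45 evaluable: 1 − 45/60 = 25%. This agrees with the 15 per group in section 6.4 (3 × 15 = 45). The 25% is back-calculated; the plan states neither a rate nor reasons. The available text gives no Aim 1 power figure to reproduce. The Aim 2 power of 0.59 cannot be reproduced because its variance and slope parameters are not given.

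**3. Power (illustration).** Inputs from section 6.4: f = 0.25, α = 0.15, m = 2 time points, ρ = 0.3, three groups. The calculation is univariate, without the IQ covariate, and uses a noncentral F with 2 and N − 3 degrees of freedom.

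- Between groups: λ = N f² m / (1 + ρ). For N = 60, 60 × 0.0625 × 2 / 1.3 = 5.77.
- Group by time: λ = N f² m / (1 − ρ). For N = 60, 60 × 0.0625 × 2 / 0.7 = 10.71.

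| N | Between groups | Group by time |
|---|---|---|
| 60 | 0.74 | 0.93 |
| 45 | 0.64 | 0.85 |
| 36 | 0.56 | 0.77 |

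The plan already accepts N = 45. The rows for 60 and 45 bound what could be regained if every lost family were tested.

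**4. Bias (illustration; none of these inputs is in the documents).** Assume no true effect, a change score with SD 1, 20 per arm, an analysis of those remaining, and a removal propensity correlated r = 0.3 to 0.5 with poor change. If a fraction p is removed, the mean change of those who remain rises by r × φ(z)/(1 − p), where z is the cut-off for p. The factor φ(z)/(1 − p) is 0.274 at 15%, 0.424 at 25% and 0.570 at 35%.

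- Equal 25% loss: each arm's mean rises by 0.424 × 0.3 = 0.13 to 0.424 × 0.5 = 0.21 SD. The shifts cancel in the contrast.
- 15% v 35%: (0.570 − 0.274) × 0.3 = 0.09, and × 0.5 = 0.15 SD.

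A simulation of the same model gave the shifts below. The type I error follows from the shift by a normal approximation with 20(1 − p) per arm. For 15% v 35% that is 17 and 13, so SE = √(1/17 + 1/13) = 0.368.

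| Loss by arm | Shift in contrast (SD) | Type I error (nominal 0.15) |
|---|---|---|
| 25% v 25% | 0 | 0.150 |
| 20% v 30% | 0.04 to 0.07 | 0.153 to 0.158 |
| 15% v 35% | 0.09 to 0.15 | 0.162 to 0.183 |
| 10% v 40% | 0.14 to 0.22 | 0.176 to 0.222 |

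**The case against.** Much can be said for the plan, and most of it limits the point without removing it.

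- Section 4.7 permits discontinuation and does not require it. A reader might infer that every non-adherent or referred family leaves the study and that all assessment then ends. The documents do not say so: 4.8 requests a battery containing one Aim 1 variable, and 3.1.5 may reach early stoppers. Loss of parents' data is likewise possible but not stated.
- The conflict between 4.6 and 4.7 exists only for referral. On non-adherence 4.6 is silent, so that part rests on 4.7 alone.
- A reader might infer that the CRT arms must lose more, because they carry 15 added sessions of 45 to 60 minutes and "Participants in CRT will be given weekly homework". Sections 1.3 and 9.4.3 point the other way: they expect CRT to improve retention. No rates by arm are given, so the direction is unknown.
- A reader might infer that the Aim 2 dose curve would come only from adherent families. Section 6.1 models change along each participant's trajectory across the 15 sessions, so early visits of families later removed still contribute. Nothing in 4.6 to 4.8 deletes them.
- Lack of improvement in 9.4.4 is not defined as lack of flexibility, and its link to parents' scores is weaker still. The 25% also includes voluntary withdrawals, which no rule can prevent, and the fidelity exclusions in 7.3.1.
- This is a target-engagement phase; section 5.2 disclaims any efficacy evaluation. Follow-up after treatment stops is a choice here. But the comparison is still between randomized arms and informs the Go/No-Go decision, so the choice should be made openly.

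**Conclusion.** The point holds in a limited form. The text conflicts on what referral ends, 4.7 gives broad discretion to discontinue from the study for poor adherence, and no section clearly secures end-of-treatment D-KEFS scores for those removed or for their parents. This allows outcome-related loss of Aim 1 data; it does not show that such loss will occur.

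The cost is chiefly power: at most the gap between 0.64 and 0.74 (between groups) or 0.85 and 0.93 (group by time) under the simplified model, if all 15 families were recovered. Bias in the contrast needs removal that is both outcome-related and unequal between arms. The 0.09 to 0.15 SD at 15% v 35% rests wholly on assumed rates and correlations, and even there type I error is about 0.16 to 0.18 against 0.15. The half-SD effect in section 6.4 is an Aim 2 slope, so it is not a proper yardstick for this shift. The change is worth making because it is small and specific, not because a large bias has been shown.

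**What to change.** Reconcile sections 4.6, 4.7 and 4.8 so that stopping trial treatment and leaving the study are separate events.

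- State that adolescents and parents who stop treatment for non-adherence or referral, and who have not withdrawn consent, are still invited to the remaining scheduled assessments. The minimum is the end-of-treatment D-KEFS and BRIEF-2, where taking part is safe and feasible.
- Apply this person by person, so that a parent can continue when the adolescent cannot, and the reverse.
- State whether 3.1.5 and 4.8 cover subjects removed by the investigator, and record the number of sessions each participant received.
- Leave the clinical criteria for stopping treatment, and the safety and administrative grounds in 4.7, unchanged.
- If remote testing is to be used for these families, extend 3.1.4. It now allows remote assessment only when presence at the hospital creates a risk, and it leaves out tasks that need objects to be handled.

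The cost is a protocol amendment with consent wording, staff time to follow off-treatment families, and partial data from those who decline. Sections 9.7.2 and 9.7.3 list payments per time point, so these visits are planned. A reader should not infer that they are funded for all 60 families, because the documents show no budget.

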4.8 Early Termination Study Visit

Subjects who withdraw from the study will be asked complete the full questionnaire battery. Should the family not wish to complete these measures, data from their last visit will serve as the last data point.

5 STUDY EVALUATIONS AND MEASUREMENTS

5.1 Screening and Monitoring Evaluations and Measurements

5.1.1 Medical Record Review

Include a listing of the variables that will be abstracted from the medical chart (paper or electronic).

- Date of birth
- Height
- Lowest weight
- Highest weight
- DSM-5 criteria for Anorexia Nervosa
- Expected body weight (i.e., target goal weight for weight restoration)
- Expected height (for those who have lost linear height)
- Date of last menstrual period (if menarche has begun)
- Parental date of birth (necessary for neuropsychological assessment)
- Race (parental and adolescent)
- Ethnicity (parental and adolescent)
- Familial history of eating disorders
- Parental height and weight
- Mid-parental height
- Hormonal levels
- Vitals
- Daily Weight
- Caloric Intake
- Medication

5.1.2 Other Evaluations, Measures

We will collect demographic information from the adolescent and parents. This includes age, date of birth, sex, race/ethnic.

5.1.2.1 *Cognitive flexibility*

Wechsler Abbreviated Scale of Intelligence (WASI;⁶⁰): The WASI is a nationally standardized measure of general intellectual functioning used in clinical, educational, and research settings that scores individuals on four subtests: Vocabulary, Similarities, Block Design, and Matrix Reasoning. We will administer the two subscale version of the WASI to calculate IQ. This is necessary to provide a context in which to understand the results of the neuropsychological testing.

Rey-Osterrieth Complex Figure Test (RCFT;⁶¹): The RCFT measures visual-spatial perception, construction, non-verbal memory, planning, problem solving, and motor function. This test is pen and paper based requiring participants to copy a complex figure. There are two important components to the recreation of the complex figure: recalling it after a brief period of time without priming and the copying it. It is valid to use in adolescents with AN.⁶² It is used as a measure of central coherence. Central coherence has been demonstrated to be impaired in some adolescents with AN.

Delis-Kaplan Executive Functioning Scales (DKEFS);⁶³ The DKEFS is a comprehensive, standardized battery of assessments of executive functioning that can be used with children and adults, ages 8–89 years. It has also been validated for use with adolescents with AN.⁶⁴ Selected subtests administered included: trail making test, verbal fluency test, color-word interference test, and sorting test.

Behavior Rating Inventory of Executive Function-2 (BRIEF-2);⁶⁵ The BRIEF-2 is an 86 item questionnaire that assesses executive functioning in children and adolescents aged 5 to 18 years of age. There is a global executive composite score as well as subordinate indices examining behavioral regulation and metacognition. The Behavioral Regulation index consists of subscales measuring inhibition, set-shifting, and emotional control. The Metacognition index consists of subscales looking at initiate, working memory, planning and organizing, organization of materials, and monitoring one's own work. Internal reliability has been found to be good with an alpha of .96 for the Behavioral Regulation Index and an alpha of .96 for the Metacognition index. Adolescents will complete this about themselves and parents will complete it about the adolescent and themselves.

5.1.2.2 Weight and Eating Disorder Symptoms

Anorectic Behavior Observation Scale (ABOS);⁶⁶ This 30-item self-report measure taps into parents' observations of their child's disordered eating behavior. This measure has good specificity (89.6%) and sensitivity (90%) in terms of parental report of ED symptoms; and it is correlated with other measures of disordered eating behavior. There are three subscales in this measure: eating behavior ($\alpha=0.80$), bulimic-like behavior ($\alpha=0.69$), and hyperactivity ($\alpha=0.69$). Good internal consistency has been found for each subscale. This measure is completed by parents and corroborates adolescent report of symptoms.

Accommodation and Enabling Scale for Eating Disorders-Revised (AESED);^{67,68} This 41-item measure gathers information about the enabling behaviors that family members with a child who has an eating disorder engage in. It is a revised version of a measure developed for use with adults. The original measure contains three subscales: avoidance and modifying routine, meal ritual, and control of the family. The original scale has internal consistency values ranging from 0.77 to 0.92. Only parents complete this measure.

Eating Disorder Examination – Questionnaire (EDE-Q);^{71,72} The EDE-Q is a 29-item questionnaire that is a self-report version of the Eating Disorder Examination (EDE). We use a self-report measure to reduce participant burden yet allow for assessment at specific time points. This measure assesses four symptom domains : restraint ($\alpha=0.75$), eating ($\alpha=0.78$), weight ($\alpha=0.67$), and shape concerns ($\alpha=0.79$) as well as the presence and severity of specific ED behaviors. This will be used to establish diagnosis and remission status. To track change over treatment and follow-up, the 28 item self-report version of the EDE will be used. Finally, to track weekly change and assess any changes in eating disorder symptomatology that might occur during medical hospitalization, a 12 item brief version of the EDE will be used. The EDE and its variants are the gold-standard in symptom assessment for eating disorders.

5.1.2.3 Behavioral Flexibility

Howe's grocery. Howe's grocery is a website that mimics an online grocery store. The store contains 8000 products across various categories (e.g., breads, produce, beverages, snack foods). Each product is an actual product with the exception of store brand "Howe's" products. Product nutrition information and price are accurate as of February 2018. By clicking "check out" consumers indicate they have finished their shopping trip. Consumers are not charged for and they do not receive any groceries. Howe's grocery has a logging framework that allows researchers have a granularity of understanding where users click, spend the most time, or the sequence of additions and removals from the user's cart. In this study, parents' food choices in their cart can be analyzed for macronutrient and caloric content. Parents will be asked to do three days of meal planning and then "shop" for those menu items on-line.

Buffet Challenge. Adolescents with AN will be presented with a buffet of food options (See Table 2). Buffet options were created in collaboration with a nutritionist and generated from items in the Food Choice Task.⁷³ We chose to present adolescents with actual food items instead of a computerized task as there may be a difference between being able to choose more varied food on a computer and actually choosing and consuming foods. Food options will include both "safe" foods (such as salad, lean protein) and common "fear" foods (pasta, pizza, desserts). Adolescents will approach the buffet, serve food, and consume the meal without coaching or support from parents. The meal will be videotaped and the following data collected: time to approach buffet, time spent serving food, time eating food, amount of food chosen (weight and calories), macronutrient profile of food chosen, and amount (calories and macronutrients) eaten. We will also code for meal time behaviors reported in Gianini⁷⁴ (e.g., tearing, staring, dissecting).

Approach-Avoidance Task (AAT): The AAT assesses approach-avoidance tendencies. Single stimuli are presented to participants on a computer screen. In response to the images, the participant presses a computer key. One key represents a positive valence, or an "approach" response, and the other represents a negative valence, or an "avoidant" response. Unique deduction of stimuli valence, which, for this study, will display as food items. With a keyboard, participants will press one of two buttons for each stimulus presented to them. The images displayed in this AAT will be that of food items (e.g., pizza and cake) or personal care items (e.g., toothbrush or towel).

**Table 2. Buffet Challenge Foods
(sample)**

grilled chicken tofu doughnuts/brownies French fries chicken fingers veggies peanut or almond butter	yogurt and granola salad bar wrap/sandwich bar chocolate mac and cheese plain pasta with red sauce pizza
--	--

